9.4.4. Clinical Safety Laboratory Assessments

- See Appendix 2 for the list of clinical laboratory tests to be performed and refer to the SoA (Section 2) for the timing and frequency.
- The investigator must review the laboratory report, document this review, and record any clinically relevant changes occurring during the study in the AE section of the eCRF. The laboratory reports must be filed with the source documents. Clinically significant abnormal laboratory findings are those that are not associated with the underlying disease, unless judged by the investigator to be more severe than expected for the participant's condition.
- All laboratory tests with values considered clinically significantly abnormal during participation in the study or within 30 days after the last dose of study treatment should be repeated until the values return to normal or baseline, or are no longer considered clinically significant by the investigator or MSP.
 - If such values do not return to normal/baseline within a period of time judged reasonable by the investigator, the etiology should be identified and the sponsor notified.
 - All protocol-required laboratory assessments, as defined in Appendix 2, must be conducted in accordance with the laboratory manual and the SoA (Section 2).
 - If laboratory values from non-protocol specified laboratory assessments performed at the institution's local laboratory require a change in participant management or are considered clinically significant by the investigator (eg, SAE or AE or dose modification), then the results must be recorded in the eCRF.

Relamorelin

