11.2 Clinical Laboratory Parameters

Clinical laboratory test values from all assessments (including those from unscheduled or repeat assessments) will be considered potentially clinically significant (PCS) if they meet either the lower-limit or higher-limit PCS criteria listed in [Table 11.2-1](#).

The number and percentage of participants who have PCS postbaseline clinical laboratory values will be tabulated by treatment group for the Treatment Period and by treatment sequence for the RW Period. The percentages will be calculated relative to the number of participants with available non-PCS baseline values and at least 1 postbaseline assessment for periods. The numerator will be the total number of participants with available non-PCS baseline values and at least 1 PCS postbaseline value by treatment group for the Treatment Period and by treatment sequence for the RW Period.

Table 11.2–1. Criteria for Potentially Clinically Significant Laboratory Tests

| Parameter | SI Unit | Lower Limit | Higher Limit |
|----------------------------------|--------------------|--------------------|---------------------|
| CHEMISTRY | | | |
| Albumin | g/L | < 0.9 * LLN | > 1.1 * ULN |
| Alanine Aminotransferase (ALT) | U/L | — | ≥ 3 * ULN |
| Alkaline Phosphatase | U/L | — | ≥ 3 * ULN |
| Aspartate Aminotransferase (AST) | U/L | — | ≥ 3 * ULN |
| Calcium | mmol/L | < 0.9 * LLN | > 1.1 * ULN |
| Chloride | mmol/L | < 0.9 * LLN | > 1.1 * ULN |
| Cholesterol | mmol/L | — | > 1.6 * ULN |
| Creatinine | μmol/L | — | > 1.3 * ULN |
| Potassium | mmol/L | < 0.9 * LLN | > 2.0 * ULN |
| Glucose, Fasting | mmol/L | < 0.9 * LLN | > 2.5 * ULN |
| Glycohemoglobin A1C | % | | Increase of ≥ 0.5% |
| Glycohemoglobin A1C | % | | Increase of ≥ 1% |
| Sodium | mmol/L | < 0.9 * LLN | > 1.1 * ULN |
| Total Bilirubin | μmol/L | — | > 1.5 * ULN |
| Total Protein | g/L | < 0.9 * LLN | > 1.1 * ULN |
| Triglycerides, Fasting | mmol/L | — | ≥ 3 * ULN |
| Urea (BUN) | mmol/L | — | > 1.2 * ULN |
| Magnesium | mmol/L | < 0.9 * LLN | > 1.1 * ULN |
| Bicarbonate | mmol/L | < 0.9 * LLN | > 1.1 * ULN |
| Phosphate | mmol/L | < 0.9 * LLN | > 1.1 * ULN |
| Uric Acid | μmol/L | < 0.9 * LLN | > 1.1 * ULN |
| HEMATOLOGY | | | |
| Basophils Absolute Cell Count | 10 ⁹ /L | — | > 3 * ULN |
| Eosinophils Absolute Cell Count | 10 ⁹ /L | — | > 3 * ULN |
| Hematocrit | Ratio | < 0.9 * LLN | > 1.1 * ULN |
| Hemoglobin | g/L | < 0.9 * LLN | > 1.1 * ULN |

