| Lymphocytes Absolute Cell Count | 10 ⁹ /L | < 0.8 * LLN | > 1.5 * ULN |
| MCH | PG | — | > 3 * ULN |
| MCHC | G/L | — | > 3 * ULN |
| MCV | fL | < 0.9 * LLN | > 1.1 * ULN |
| Monocytes Absolute Cell Count | 10 ⁹ /L | — | > 3 * ULN |
| Neutrophils Absolute Cell Count | 10 ⁹ /L | < 0.8 * LLN | > 1.5 * ULN |
| Platelet Count | 10 ⁹ /L | < 0.5 * LLN | > 1.5 * ULN |

Table 11.2–1. Criteria for Potentially Clinically Significant Laboratory Tests

| Parameter | SI Unit | Lower Limit | Higher Limit |
|--|---------------------|--------------------|---------------------|
| Red Blood Cell Count (Erythrocyte Count) | 10 ¹² /L | < 0.9 * LLN | > 1.1 * ULN |
| White Blood Cell Count | 10 ⁹ /L | < 0.7 * LLN | > 1.5 * ULN |
| URINALYSIS | | | |
| pH | | < 0.9 * LLN | > 1.1 * ULN |
| Specific Gravity | | — | > 1.1 * ULN |

LLN: Lower limit of normal value provided by the laboratory.

ULN: Upper limit of normal value provided by the laboratory.

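### The upper potassium limit in SAP Table 11.2-1 (> 2.0 × ULN) is practically out of reach, so the laboratory table cannot show high potassium

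*SAP*

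**What the plan says.** SAP 11.2 classes laboratory results by multiples of the reference limits. Values "will be considered potentially clinically significant (PCS) if they meet either the lower-limit or higher-limit PCS criteria" of Table 11.2-1. The potassium row reads "Potassium | mmol/L | < 0.9 * LLN | > 2.0 * ULN". The sodium row reads "Sodium | mmol/L | < 0.9 * LLN | > 1.1 * ULN", and chloride, calcium, magnesium, bicarbonate and phosphate carry the same pair of multipliers as sodium. The footnote leaves the reference limit to the laboratory: "ULN: Upper limit of normal value provided by the laboratory". No number for potassium appears in either document.

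On reporting, the section states: "The number and percentage of participants who have PCS postbaseline clinical laboratory values will be tabulated by treatment group", and by sequence in the randomized-withdrawal period. It adds: "The numerator will be the total number of participants with available non-PCS baseline values and at least 1 PCS postbaseline value". SAP 11.2 plans no other laboratory table.

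**The concern.** Seven electrolytes share one lower multiplier. Six share one upper multiplier, and potassium alone departs from it, without a stated reason. Variation in multipliers is not itself a fault, because the table uses values from 1.1 to 3. The question is whether a potassium value above twice the upper reference limit could plausibly occur often enough for the criterion to do any work.

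If it could not, the potassium row would appear to cover both directions while in effect counting only low values. A near-zero contribution from the high side could then be read as evidence that high potassium did not occur, when the limit was simply too far away to register it. The loss is a between-group comparison of high potassium at a fixed limit.

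**Working it through.** **1. Position of the row in the table.** Counting Table 11.2-1 by hand:

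- 34 rows have an upper limit that is a multiple of ULN: 1.1 in 15, 1.2 in 1, 1.3 in 1, 1.5 in 5, 1.6 in 1, 2.0 in 1 (potassium), 2.5 in 1 (fasting glucose) and 3 in 9.
- 20 of these also have a lower limit. Their upper multipliers are 1.1 in 14, 1.5 in 4, 2.0 in 1 and 2.5 in 1, so 14 + 4 = 18 of 20 are at most 1.5.
- 16 of the 20 use a lower limit of 0.9 × LLN. Of those, 14 have an upper limit of 1.1 × ULN. The two exceptions are potassium and fasting glucose, the latter written as "Glucose, Fasting | mmol/L | < 0.9 * LLN | > 2.5 * ULN".

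**2. The limit in mmol/L.** Formula: limit = multiplier × ULN. The ULN values are assumptions. The last column shows how far a value of 8.0 mmol/L would fall short of a multiplier of 2.0.

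| Assumed ULN | 2.0 × ULN | 1.1 × ULN | 8.0 / ULN |
|---|---|---|---|
| 4.5 | 9.0 | 4.95 | 1.78 |
| 5.0 | 10.0 | 5.5 | 1.60 |
| 5.5 | 11.0 | 6.05 | 1.45 |
| 6.0 | 12.0 | 6.6 | 1.33 |

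At none of these ULN values would 8.0 mmol/L be flagged.

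**3. Expected number flagged.** This is an illustration, not a prediction. It assumes normally distributed values, an LLN of 3.5 mmol/L, a reference interval that holds the central 95%, one value per participant, and the planned 480 participants per arm (SAP 13). Let k be a factor inflating the SD and s an upward shift in the mean:

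- mean = (LLN + ULN)/2 and SD = (ULN − LLN)/(2 × 1.96)
- z = (multiplier × ULN − mean − s)/(k × SD)
- expected flags = 480 × P(Z > z)

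For ULN 5.0: mean = 4.25, SD = 1.5/3.92 = 0.383, and z = (10.0 − 4.25)/0.383 = 15.0. For ULN 5.5: mean = 4.50, SD = 2.0/3.92 = 0.510, and z = (11.0 − 4.50)/0.510 = 12.7.

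| k, s (mmol/L) | ULN | z at 2.0 | Flags at 2.0 | z at 1.1 | Flags at 1.1 |
|---|---|---|---|---|---|
| 1, 0 | 5.0 | 15.03 | < 0.001 | 3.27 | 0.26 |
| 1, 0 | 5.5 | 12.74 | < 0.001 | 3.04 | 0.57 |
| 1, 0.5 | 5.0 | 13.72 | < 0.001 | 1.96 | 12 |
| 1, 0.5 | 5.5 | 11.76 | < 0.001 | 2.06 | 9.5 |
| 3, 0.5 | 5.0 | 4.57 | 0.0012 | 0.65 | about 120 |
| 3, 0.5 | 5.5 | 3.92 | 0.021 | 0.69 | about 120 |

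The largest figure at 2.0 is about 0.02 participants per arm, and it needs a tripled spread and a raised mean. SAP 11.2 counts any postbaseline value, so repeated sampling raises this. Even ten values per participant (an assumption) would give at most 10 × 0.021 = 0.21. At 1.1 × ULN, by contrast, the count moves from below 1 to double figures or close to it when the mean shifts by 0.5 mmol/L. That is what a between-group table needs.

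**4. What else would show a difference.** Protocol 9.4.4 has the investigator "record any clinically relevant changes occurring during the study in the AE section of the eCRF", and SAP 11.1 tabulates adverse events by preferred term. SAP 15.3 lists every assessment. The first depends on individual judgement and the second is not a summary. Neither gives a group count at a common threshold.

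**The case against.** The case on the other side has four parts.

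- **The outlier count depends on the subset.** Over all 34 ULN-based rows, 11 have a multiplier of 2.0 or more (1 + 1 + 9). Having a lower limit is no reason in itself for a smaller upper one, and fasting glucose is two-sided at 2.5. This is right: the counts describe the table and do not prove an error, and the documents cannot show whether 2.0 is a slip or intended. The point rests on attainability, not on the count.
- **Equal multipliers are not equal stringency.** With an assumed sodium range of 135–145 mmol/L, the mean is 140, the SD is 10/3.92 = 2.55, and 1.1 × ULN = 159.5 lies (159.5 − 140)/2.55 = 7.6 SD above the mean. For potassium, 1.1 × ULN lies about 3.0–3.3 SD above. Matching the other electrolytes is therefore not enough to justify 1.1. That also stands. The better reason for 1.1 is that it puts the potassium limit at an attainable 5.5–6.05 mmol/L, and another justified limit would serve as well.
- **The expected count rests on assumptions.** It does: the ULN is the laboratory's, and the tail calculation adds a distribution. The conclusion nevertheless holds in every scenario tried.
- **Safety is covered elsewhere.** Low potassium is still flagged, all values are listed, clinically relevant changes become adverse events, and protocol 10.3.5 provides a safety monitoring board. This limits the consequence but does not supply the missing count.

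**Conclusion.** The concern holds, as a minor point. The reading of the table and the absence of a stated reason are certain. The size depends on the assumed ULN: > 10.0–11.0 mmol/L for 5.0–5.5 mmol/L, and > 9.0–12.0 mmol/L for 4.5–6.0 mmol/L. Under the normal-tail illustration, the upper criterion would flag at most about 0.02 participants per 480 at one value each. The potassium row, followed as written, is therefore uninformative about high values, whether or not high and low counts are displayed separately.

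The effect is confined to one row of a descriptive table. SAP 4 and 16 declare an abbreviated report after early termination, protocol 12.4.1 does not list potassium among the events of special interest, and no efficacy result depends on it.

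**What to change.** In Table 11.2-1, change the upper potassium limit to > 1.1 × ULN, or state another attainable reporting limit with a reason. If 2.0 was intended, give the reason and add an attainable limit beside it. Run or rerun the PCS table. If that table has already been produced, label the change post hoc and keep the count at 2.0 × ULN next to the new one. Check the MCH, MCHC and urine specific gravity rows for attainability as well and, in light of the sodium illustration, the upper sodium limit. It would also help to say whether high and low counts are shown separately.

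The cost is a SAP revision, one table entry, one program parameter and at most one rerun. Revision is feasible: the current SAP already amends one dated 1 October 2020. There are three side effects:

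- Some haemolysed samples may be flagged (an assumption).
- Participants above the new limit at baseline leave the denominator, because the percentage is restricted to those not PCS at baseline.
- The documents do not show whether the lead-in studies use the same criteria. Keeping the 2.0 count preserves any such comparison.

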11.3 Vital Signs

A listing for vital signs (heart rate (HR), respiratory rate, systolic and diastolic blood pressure (BP), temperature, and body weight) at each visit will be presented.

11.4 Electrocardiogram

A listing for electrocardiographic (ECG) parameters (HR, RR interval, PR interval, QRS interval, QT interval, and QTc) at each assessment time point will be presented. The QTc will be calculated using Fridericia and/or Bazett correction.

11.5 COVID-19

A listing of participants with visits impacted due to COVID-19 for the ITT population will be provided.

12 **Interim Analysis**

No interim analysis is planned for this study.

13 Determination of Sample Size

The study is early terminated; and the original study primary objectives are no longer applicable. The original study design considers the enrollment of this study depending upon the drop-out rates in the pivotal studies RLM-MD-01 and RLM-MD-02. Assuming 300 participants per arm in each study and a drop-out rate of 20% in each of the pivotal studies, it is expected that approximately 960 participants (480 participants in each arm) will enter the study. Further, assuming that the drop-out rate will also be 20% by Week 12 in this study, it is expected that there will be 384 participants per treatment group at Week 12. This sample size will provide 99% power to detect a statistically significant difference in response rate between treatment and placebo in both the 4-symptom composite DGSSS endpoint (assuming a placebo rate of 14% and a treatment rate of 35%) and in the vomiting response endpoint (assuming a placebo rate of 11% and a treatment rate of 26%) at Week 12. The assumed response rates were those calculated from study RM-131-009.

14 **Statistical Software**

Statistical analyses will be performed using version 9.4 (or newer) of SAS on a Linux operating system.

15 Data Handling Conventions

15.1 Analysis Weeks and Visit Time Windows for Efficacy Analysis

15.1.1 Analysis Weeks for Efficacy Analysis

Table 15.1.1–1 below presents the analysis weeks assigned for the efficacy analysis of the participant daily diary data related to DGSSD. These analysis weeks will be used in the calculations for all week-based endpoints (eg, weekly DGSSS, weekly vomiting frequency, individual symptoms weekly scores etc.).

Table 15.1.1–1. Analysis Time Windows for Efficacy Analysis

| Period | Analysis Week | Begins | Ends | |
|------------------|----------------------|---|------------------------------------|--|
| Treatment Period | Week 1 | Day 1, Day 84 of lead-in studies RLM-MD-01/02 | Day 7 | |
| | Week 2 | Day 8 | Day 14 | |
| | Week 3 | Day 15 | Day 21 | |
| | Week 4 | Day 22 | Day 28 | |
| | Week 5 | Day 29 | Day 35 | |
| | Week 6 | Day 36 | Day 42 | |
| | Week 7 | Day 43 | Day 49 | |
| | Week 8 | Day 50 | Day 56 | |
| | Week 9 | Day 57 | Day 63 | |
| | Week 10 | Day 64 | Day 70 | |
| | Week 11 | Day 71 | Day 77 | |
| | Week 12 | Day 78 | Day 84 | |
| | | | | |
| | Week k | Day (k-1)x7 + 1 | Day k x 7 | |
| | | | | |
| | Week 40 | Day 274 | Day 280 (or Day of last dose) | |
| RW | Week 1 | RW Day 1, the day of re-randomization | RW Day 7 | |
| | Week 2 | RW Day 8 | RW Day 14 | |
| | Week 3 | RW Day 15 | RW Day 21 | |
| | Week 4 | RW Day 22 | RW Day 28 | |
| | Week 5 | RW Day 29 | RW Day 35 | |
| | Week 6 | RW Day 36 | RW Day 42 (or Day of last RW dose) | |

For the RW Period, diary day is calculated as (diary date - date of re-randomization + 1). For the Treatment Period, diary day is calculated as (diary date – the date of Day 1 in Treatment Period + 1).

15.2 Derived Efficacy Variables

Weekly scores for nausea, abdominal pain, postprandial fullness, bloating, vomiting severity and early satiety will be the average of the corresponding non-missing daily scores if a participant has at least 4 non-missing daily scores during each week (See section 15.1 for definition of analysis weeks). Weekly score will be set to missing if there are less than 4 days with non-missing diary data during a week.

Weekly DGSSS is derived as the sum of the weekly DGSSD items of nausea, abdominal pain, postprandial fullness, and bloating. The range of DGSSS is from 0 to 40 with 40 indicating the worst possible. If any one of weekly items of nausea, abdominal pain, postprandial fullness, and bloating, is missing, then the weekly DGSSS will be set to missing.

Weekly assessment for vomiting frequency is calculated as the total number of vomiting episodes during a week (normalized for the number of days with non-missing responses). i.e.:

$$\text{Weekly number of vomiting episodes} = (\text{total number of vomiting episodes in the week}) * (7 \text{ days} / (\text{number of days with non-missing responses in the week})).$$

The weekly number of vomiting episodes is set to missing if there are less than 4 days with non-missing diary data during the week.

15.3 Repeated or Unscheduled Assessments of Safety Parameters

All postbaseline assessments will be used for PCS value determination, and all assessments will be presented in the data listings.

15.4 Missing Date of the Last Dose of Study Treatment

When the date of the last dose of study drug is missing in specific period, all efforts should be made to obtain the date from the Investigator. If it is still missing after all efforts have been made, the last diary date in the specific period will be used as the last dose date.

15.5 Missing Severity Assessment for Adverse Events

If severity is missing for an AE that started before the date of the first dose of study drug product, an intensity of mild will be assigned. If severity is missing for an AE that started on or after the date of the first dose of study drug, an intensity of severe will be assigned. The imputed values for severity assessment will be used for the incidence summary; the values will be shown as missing in the data listings.

15.6 Missing Date Information for Adverse Events

The following imputation rules apply to cases in which the start date is incomplete (ie, partial missing) for AEs.

Missing day and month

- If the year is the same as the year of the date of the first dose of study drug, then the day and month of the date of the first dose of study drug will be assigned to the missing fields.
- If the year is prior to the year of the date of the first dose of study drug, then December 31 will be assigned to the missing fields.
- If the year is after the year of the date of the first dose of study drug, then January 1 will be assigned to the missing fields.

Missing month only

- The day will be treated as missing and both month and day will be replaced according to the above procedure.

Missing day only

- If the month and year are the same as the month and year of the date of the first dose of study drug, then the date of the first dose of study drug will be assigned to the missing day.
- If either the year is before the year of the date of the first dose of study drug or if both years are the same but the month is before the month of the date of the first dose of study drug, then the last day of the month will be assigned to the missing day.
- If either the year is after the year of the date of the first dose of study drug or if both years are the same but the month is after the month of the date of the first dose of study drug, then the first day of the month will be assigned to the missing day.

If the stop date is complete and the imputed start date as above is after the stop date, the start date will be imputed by the stop date.

If the start date is completely missing and the stop date is complete, then the following algorithm is used to impute the start date:

- If the stop date is after the date of the first dose of study drug, the date of the first dose of study drug will be assigned to the missing start date.
- If the stop date is before the date of the first dose of study drug, the stop date will be assigned to the missing start date.

16 Changes to Analyses Specified In Protocol

The study was early terminated and only an abbreviated study report will be applied to this study, for which only minimum efficacy analyses will be implemented. As such, this document is an abbreviated statistical analysis plan for only selected study disposition, demographics, safety parameters and selected descriptive efficacy analyses.

17 **References**

There are no references.

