11.1 Adverse Events

Adverse events will be coded by system organ class and preferred term using the *Medical Dictionary for Regulatory Activities (MedDRA)*, version 23.0 or newer.

An AE will be considered a treatment-emergent adverse event (TEAE) for the study if it was present after the first dose of study intervention or was present before the date of the first dose of study intervention and increased in severity or became serious after the first dose of study treatment during the study. Per case report form instructions, a new AE record will be created with a new AE onset date for any AE that worsens. Therefore, TEAEs can simply be identified as those AEs with recorded onset date on or after the date of the first dose of study intervention and within 30 days of the last dose of study intervention in the study. An AE that occurs more than 30 day after the last dose of study drug in the study will not be counted as a TEAE for the study.

An AE will be considered a treatment-emergent SAE (TESAE) if it is a TEAE that also is an SAE.

All TEAEs related summary will be presented by treatment group for the Treatment Period and by treatment sequence for the RW Period separately. A TEAE will only be counted in the double-blind treatment period if it starts between the date of the first dose of study treatment (inclusive) in the double-blind treatment period and the date of the first dose of study treatment (exclusive) in the RW period or within 30 days of the date of the last dose of study treatment in the double-blind treatment period if the patient did not enter the RW period. A TEAE will only be counted in the RW period if it starts on or after the first dose of study treatment in the RW period and within 30 days of the date of the last dose of study treatment in the RW period.

The number and percent of participants with TEAEs, TEAEs leading to discontinuation from study, Deaths, SAEs and TESAEs will be presented by treatment group for the Treatment Period, and by treatment sequence for the RW Period separately.

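### Partial adverse-event start dates are imputed only against the first study dose, so a share of randomized-withdrawal events is counted in the Treatment Period

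*SAP*

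**What the plan says.** SAP 15.6 completes an incomplete AE start date as follows.

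- **Day and month missing.** When the event falls in the calendar year of that first dose, the rule reads: "then the day and month of the date of the first dose of study drug will be assigned to the missing fields". For a later year, "then January 1 will be assigned to the missing fields".
- **Day missing.** In the month of the first dose, the first-dose date is used. In a later month, "then the first day of the month will be assigned to the missing day".
- **Start wholly missing, stop date after the first dose.** In this case "the date of the first dose of study drug will be assigned to the missing start date".
- **Stop-date check for partial dates.** "If the stop date is complete and the imputed start date as above is after the stop date", the stop date replaces the imputed start.

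The only anchor is the first dose of study drug. Neither the first RW dose nor the re-randomization date appears in 15.6.

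SAP 11.1 then splits events by period. An event counts in the RW Period only "if it starts on or after the first dose of study treatment in the RW period and within 30 days" of the last RW dose. An event that starts from the first Treatment Period dose up to, but not including, the first RW dose counts in the Treatment Period. Treatment Period tables are by treatment group and RW tables are by treatment sequence. SAP 6.5 defines three sequences: Placebo - 10 µg, 10 µg - 10 µg and 10 µg - Placebo.

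**The concern.** The imputation rule and the period rule use different reference dates. At the first study dose, 15.6 resolves an ambiguous month toward the dose, so the event becomes treatment-emergent. At the first RW dose, which is the second point where treatment can change, it resolves the same ambiguity to a date before the dose. The stop-date check can only move a start date earlier, so it never returns an event to the RW Period.

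In the Placebo - 10 µg sequence, an event that began on relamorelin is then tabulated under placebo. In the 10 µg - Placebo sequence, an event that began on placebo is tabulated under relamorelin. In the 10 µg - 10 µg sequence the period is wrong but the treatment is right. These tables matter because the abbreviated SAP still produces them: TEAEs, SAEs, discontinuations, severity and related events, by treatment group and by sequence.

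**Working it through.** The documents give no figure on this point, so there is nothing of theirs to reproduce.

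**Inputs from the SAP.** The Treatment Period lasts 40 weeks (280 days) and the RW Period 6 weeks (42 days) (4.1). The RW window extends 30 days past the last RW dose, so up to 42 + 30 = 72 days (11.1). Planned arms are 480 and 480. The relamorelin arm is re-randomized 1:1 and the whole placebo arm switches to relamorelin (4.1).

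**Assumptions.** First-dose dates are spread evenly over a four-year calendar cycle (1,461 dates). The first RW dose is 280 days later. Onset is uniform over 42 days, uniform over 72 days, or front-loaded over 42 days (exponential weights, mean 14 days).

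**Formula.** Share misplaced = (number of date pairs with imputed start < first RW dose) / (all pairs of first-dose date and RW onset day).

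| What is missing | Uniform, 42 days | Uniform, 72 days | Front-loaded |
|---|---|---|---|
| Day | 35% | 20% | 61% |
| Day and month | 94% | 90% | 97% |
| Whole start date, stop date known | 100% | 100% | 100% |

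A missing-day event is misplaced only when its onset falls in the calendar month of the first RW dose and that dose is not on the 1st. On average 14.7 RW days qualify: 14.7/42 = 35% and 14.7/72 = 20%. For year-only dates the figure is 39.5 of 42 days, or 94%.

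**Example.** First dose 10 January 2019, first RW dose 17 October 2019, event on 22 October 2019. With the day missing, the start becomes 1 October. With day and month missing, it becomes 10 January. Both are counted in the Treatment Period.

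**Share under the wrong treatment.** Treatment changes for 480 + 240 = 720 of 960 planned participants, or 75%. If retention and AE rates are equal across sequences, 0.75 × 35% = 26% of missing-day RW events and 0.75 × 94% = 71% of year-only RW events are reported under a treatment not being taken at onset.

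**Share of all RW events.** If 2% to 5% of events lack the day (an assumption; the documents give no rate), 0.351 × 2% = 0.7% to 0.351 × 5% = 1.8% of RW events are misplaced for this reason.

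**Cost of an RW anchor.** With a constant daily event rate, this compares RW onset-days recovered per participant with Treatment Period onset-days wrongly moved into RW.

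| What is missing | Recovered | Wrongly moved, no stop-date check | Wrongly moved, with stop-date check |
|---|---|---|---|
| Day | 14.7 | 14.7 (5.3% of 280) | 6.1, 10.6 or 14.7 for events lasting 7, 14 or 30 days |
| Day and month | 39.5 | 172.3 | 6.9 to 28.7 for events lasting 7 to 30 days with a complete stop date |

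Without a check, the year-only anchor moves 172.3/39.5 = 4.4 times as many onset-days as it recovers. With a complete stop date on or after the first RW dose, it recovers more than it misplaces at these durations. For missing-day events the check leaves the anchor no worse than even.

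**The case against.** **The first dose might be meant per period.** SAP 15.4 says explicitly when it works within a specific period, and 11.1 names the RW Period. Section 15.6 does neither. Even on that reading, it gives no way to choose the period before the date is imputed.

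**A reader might infer that the rule hides relamorelin harm.** The documents do not support this. Misplacement adds relamorelin-onset events to the placebo Treatment Period column and placebo-onset events to the relamorelin one. The net direction depends on event rates that are not given.

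**A reader might infer that many events are affected.** The percentages are shares of partial-date RW events only. The SAP states neither how often dates are partial nor how many participants reached the RW Period before early termination. Participants are counted once per preferred term (SAP 11.1), so a moved event does not always change a count. Protocol 9.2.1 requires SAEs to be reported within 24 hours, which makes partial dates less likely for the most serious events. The tables are descriptive. All of this stands and limits the importance of the point.

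**Section 15.6 works for treatment emergence at study level.** This is true. It omits a second anchor and does not contradict a stated rule. Followed literally, however, it still puts RW events in the wrong period.

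**An RW anchor can replace one error with another.** This also stands. Unrestricted, it breaks even for missing-day events and is clearly worse for year-only events. The repair needs a stop-date condition.

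**Conclusion.** The point holds. Followed as written, SAP 15.6 places about 35% of missing-day RW events in the Treatment Period (20% if onset is spread over 72 days), about 94% of year-only RW events, and all RW events with a wholly missing start date and a known stop date. In the two sequences that switch treatment, 75% of planned participants, these are counted under a treatment not being taken at onset. The shares rest on evenly spread first-dose dates, RW dosing at day 280 and uniform onset. Early-clustered onset raises the missing-day share to 61%. The absolute number cannot be computed from the documents and is probably small. Neither a bias in favour of relamorelin nor a material change to the safety conclusions can be inferred.

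**What to change.** For participants who received an RW dose, add a second step to SAP 15.6.

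1. **Day missing, known month and year equal to those of the first RW dose.** Impute the first RW dose date, unless a complete stop date precedes that dose.
2. **Day and month missing, year equal to that of the first RW dose.** Impute the first RW dose date only if a complete stop date falls on or after that dose. Otherwise keep the current rule.
3. **Listing.** Flag every AE of these participants whose partial or missing start date fits both periods, including wholly missing start dates.

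The cost is one added rule, a few lines of programming and a listing flag. The downside is that some late Treatment Period events with partial dates move to the RW Period. For missing-day events this can equal the number recovered when events last 30 days or more or are ongoing, and is smaller when they are shorter. Year-only events that are ongoing or lack a complete stop date stay under the current rule, so the flag is needed to show them.
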